**Safety:**

Safety evaluations will be based on listed AEs, physical examinations, vital signs, clinical laboratory evaluations, ECGs and prior/concomitant medications, and assessment for the presence of RCL antibodies. The AE severity will be described using National Cancer Institute (NCI) Common Terminology Criteria for Adverse Events (CTCAE) grades, using the current version at study start. AEs will be coded using the Medical Dictionary for Regulatory Activities (MedDRA; version 23.0 or later) and described by body system and preferred term, relationship to FCX-013, seriousness, and severity. AEs causing investigational product discontinuation and/or early study discontinuation, and serious adverse events (SAEs) will be noted.

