#### **7.5. Dose Adjustment Criteria**

##### **7.5.1. Safety Criteria for Adjustment or Stopping Doses**

An objective of this study is to generate a safety profile of FCX-013 plus veledimex in subjects with moderate to severe localized scleroderma/morphea. To minimize risk, cumulative safety data will be reviewed by the Medical Monitor. Events that will result in immediate enrollment discontinuation and treatment discontinuation for all subjects are a positive RCL assay and histologically confirmed cancer in combination with the presence of viral vector in the tumor. In addition, the Medical Monitor may interrupt study dosing and/or study entry at any time if medically indicated.

Occurrence of any of these observations will trigger a temporary suspension of FCX-013 plus veledimex administration pending a safety investigation:

- A treatment emergent SAE or suspected SAE related to FCX- 013, the FCX-013 administration procedure, veledimex administration or any other protocol procedure.
- A positive RCL quantitative polymerase chain reaction (qPCR) assay result. A positive RCL qPCR assay will result in suspension of FCX-013 administration. The result will be confirmed by conducting a biological-based assay. If both assays are positive, FCX-013 administration will be discontinued and no further enrollment into the study will be allowed.
- An autoimmune response determined by the Investigator to be possibly, probably or definitely related to treatment.
- Any systemic infection designated as suspected to be related to FCX-013.
- A treatment emergent uncontrolled bacterial, viral, or fungal infection in a lesion that was administered by investigational product (IP) where product sterility testing results reported post injection were positive for contamination.
- Any subject diagnosed with a histologically proven skin cancer (including sarcomas) will be biopsied and assayed for viral vector by qPCR. A positive result for viral vector will cause product administration to be suspended.
- Abnormal laboratory value(s) or clinically significant change from screening/baseline that pose a risk to safe participation.
- Abnormal test procedure result(s) or clinically significant change from screening/baseline that pose a risk to safe participation (e.g., Grade 2 or above Common Terminology Criteria for Adverse Events/CTCAE criteria (v.4.03) for ECG test).

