### 12.2.3. Relationship of Adverse Event to Investigational Product

The relationship of an AE to IP is to be assessed by the PI using good clinical judgement and according to the following definitions:

- Not Related – no temporal association or the cause of the event has been identified, or the drug cannot be implicated based upon available information.
- Possibly Related – temporal association, but other etiologies are likely to be the cause. However, involvement of the drug cannot be excluded, based upon available information.
- Definitely Related – established temporal or other association (e.g., re-challenge) and event is not reasonably explained by the subject's known clinical state or any other factor, based on available information.

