### **13.4. Safety Analyses**

Subject demographics and relevant baseline data will be listed and described. Inclusion and exclusion criteria ensure that participants are suitable for the study. Premature termination will be described.

Physical examinations, vital signs, ECG data, concomitant medications, and laboratory results, including RCL analyses will be listed, and relevant changes will be described by subject and overall, as applicable.

Adverse events will be coded using the Medical Dictionary for Regulatory Activities (MedDRA) AE dictionary. Adverse events will be grouped into pre-treatment AEs and TEAEs and will be described by preferred terminology and by body system. The number of adverse event entries, as well as the number of subjects will be described, including by AE type, relationship to FCX-013 plus veledimex, seriousness, and severity of AEs.

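### The suspension criteria in Section 7.5.1 need causality by product and procedure and a 'probably' grade, but the AE record holds one rating against IP on a scale without that grade

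*Protocol*

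**What the plan says.** Protocol Section 7.5.1 lists observations that temporarily suspend FCX-013 plus veledimex administration. Three depend on causality:

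- SAEs: a treatment-emergent or suspected SAE attributed to the cells themselves or to "the FCX-013 administration procedure, veledimex administration or any other protocol procedure".
- Autoimmune events: "An autoimmune response determined by the Investigator to be possibly, probably or definitely related to treatment".
- Infections, where the wording names one product only: "Any systemic infection designated as suspected to be related to FCX-013".

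Section 12.2 makes the investigator assign one causality attribute to every AE, its relationship to the IP. Section 12.2.3 says "The relationship of an AE to IP is to be assessed by the PI" and gives three grades: *Not Related*, *Possibly Related* and *Definitely Related*.

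The planned AE summaries use different objects. The Synopsis (Safety) describes AEs by "relationship to FCX-013, seriousness, and severity". Section 13.4 describes them by "relationship to FCX-013 plus veledimex, seriousness, and severity of AEs".

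**The concern.** The criteria that pause dosing and the field that records causality should use the same terms. Here they differ in what is rated and in how it is graded.

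Safety is the primary objective, the study has one arm of about 10 subjects, and the treatment has two different components: a single session of intradermal cell injections and 14 days of an oral drug. With no comparator, the investigator's attribution is one of the few pieces of structured information on where an event came from. A rating that merges the two products and omits procedures loses it. The DSMB, which under Section 7.7 may recommend dose or regimen changes, would then have to work from narratives where a coded attribution could have been available.

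**Working it through.** No figure is involved, so the check sets the sections side by side.

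**Sources of relatedness**

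| Source named in the SAE criterion (7.5.1) | Rated under 12.2 and 12.2.3? |
|---|---|
| FCX-013 | Yes, as IP |
| FCX-013 administration procedure | No |
| Veledimex | As IP, if IP means both products; otherwise no |
| Any other protocol procedure | No |

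Four sources against one rating. Two of the four have no rating. The other two share one if IP means the combination. Section 12.2.3 does not say what IP means. The Synopsis and Table 1 apply the term to both products, while Section 11.1.1 uses it for the cell suspension alone.

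**Procedures.** *Not Related* in Section 12.2.3 includes the case where the cause of the event has been identified. Appendix 2 makes anesthesia, possibly with conscious sedation, a step of product administration. Suppose a subject has an SAE after dosing that the investigator attributes to the sedation. Its cause is identified and is neither the cells nor veledimex, so *Not Related* to IP is a proper entry. The same event falls under the administration-procedure limb of Section 7.5.1. The same holds for a biopsy taken after dosing, such as the optional persistence biopsies of years 1 to 5 in the notes to Table 4. The manufacturing biopsies are normally taken before dosing, so an SAE from them would usually not be treatment-emergent.

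**Grades**

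| Autoimmune criterion (7.5.1) | Scale (12.2.3) |
|---|---|
| possibly | *Possibly Related* |
| probably | no such grade |
| definitely | *Definitely Related* |

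Three positive grades against two. The definitions do not cover the missing middle:

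- *Possibly* is defined as "temporal association, but other etiologies are likely to be the cause", so it does not describe an event for which treatment is the likeliest cause.
- *Definitely* needs an established association and no other reasonable explanation.
- *Not Related* needs no temporal association, another identified cause, or no basis for implicating the drug.

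An event for which treatment is likelier than any alternative, but another explanation remains reasonable, meets none of the three. The investigator must grade it down to *Possibly* or up to *Definitely*.

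**Effect on the triggers**

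- Autoimmune response: both grades that can be recorded are in the criterion, so every grade except *Not Related* still suspends dosing.
- SAE related to either product: the criterion is an either-or list and the suspension covers both products. If IP means both, an SAE rated related to IP meets it whichever product was responsible.
- SAE related to a procedure: the criterion applies, but the causality field does not show it.

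**The case against.** The strongest reply is that nothing makes Section 7.5.1 run from a coded field. Section 12.2.1 sends every SAE to the sponsor within 24 hours whether or not it appears related to IP. Section 12.2 requires every AE to be fully documented. The Medical Monitor and the DSMB review cumulative safety data, the Medical Monitor may interrupt dosing at any time, and DSMB approval is needed after each of the first three subjects. With about 10 subjects, each SAE should be seen individually. This stands. A reader might infer that the triggers cannot be operated from the data collected; the documents do not support that.

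Two other strong readings fail. The missing *probably* grade does not disable the autoimmune criterion, because the grades on either side of it also meet it. A veledimex-related SAE does not escape the SAE criterion if IP means both products.

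It can also be said that anesthesia is part of the administration instructions, so an investigator might count it as IP; that a split rating records opinion and cannot isolate component effects when every subject receives both; and that the SAE forms, left to the Study Procedures Manual, may already collect more. The first shows that two investigators could code the same event differently, which is itself a reason to clarify. The second is fair: separate ratings would be judgments, though the single rating is a judgment too and carries less information. The third cannot be checked here; the protocol text requires only one attribute.

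**Conclusion.** The mismatch is real and should be corrected. Its size is four named sources against one rating, three positive grades against two, one class of event with no fitting grade, and two summary descriptions with different objects. As written, procedure-related events are not identifiable in the coded safety data, some events will be misgraded, and the causality field does not correspond to the suspension criterion it should support.

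The harm is to the quality of the primary safety data, not a failure of the triggers. The differing Synopsis wording is a smaller matter: a reader might infer that veledimex-only events would have no related category, but a one-line description in a Synopsis that itself names the combination as the product does not establish that.

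The conclusion takes Sections 12.2 and 12.2.3 as the full causality requirement. If IP there means the cells alone, the gap is wider, because veledimex causality is then not recorded. If the CRF or SAE forms already split causality, the remaining work is to align the protocol text.

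**What to change.** - In Sections 12.2 and 12.2.3 and on the AE CRF page, record causality separately for FCX-013, the FCX-013 administration procedure (including its anesthesia or sedation), veledimex, and other protocol procedures. State what IP means where the term is kept.
- Revise the grade definitions in Section 12.2.3 so that every degree of relatedness has a place, including treatment as the likeliest but not established cause.
- Reconcile the grades in Section 12.2.3 with those in Section 7.5.1. How the suspension criterion should read is for the sponsor to decide.
- Use the same relationship terms in the Synopsis and Section 13.4.

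The cost is an amendment to the wording, three more causality fields (four instead of one), and slightly more investigator time per AE. No visit, test or additional subject is needed.

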#### **7.5.2. Early Cessation of Study Treatment for an Individual**

Subjects may voluntarily stop receiving treatment at any time.

Unless a subject withdraws consent, subjects who voluntarily cease to receive treatment will continue to be followed as per the trial protocol and clinical assessment schedule to ensure that full data are obtained.

The Primary Investigator and/or the Sponsor may decide that early cessation of treatment is warranted for any one of the following reasons:

- Occurrence of AEs that pose a risk to safe participation
- Abnormal laboratory value(s) that pose a risk to safe participation
- Abnormal test procedure result(s) that pose a risk to safe participation
- Unsatisfactory therapeutic effect
- Condition no longer requires treatment
- Pregnancy

Subjects can withdraw from the study for any reason including worsening disease and to receive rescue therapy/standard-of-care treatment for worsening disease.

For subjects who are lost to follow-up, the Investigator should show due diligence by documenting in the source documents the steps taken to contact the subject (e.g., dates of telephone calls, emails).

#### **7.6. Study Termination**

Fibrocell reserves the right to terminate the study, according to the study contract. The investigator should notify the Institutional Review Board (IRB) in writing of the trial's completion or early termination and send a copy of the notification to Fibrocell.

#### **7.7. Safety Oversight: Data Safety Monitoring Board**

A DSMB will be comprised of two clinicians with expertise in dermatology and/or scleroderma, and a statistician. The DSMB will facilitate the management and identification of potential safety concerns that could affect the safety of study subjects and will evaluate the overall progress of the study through the Treatment Period. To minimize risk, cumulative safety data will be reviewed by the DSMB. Principal investigators (PIs), additional sub-investigators (Sub-Is) and scientific personnel may participate in reviews, as appropriate.

The DSMB has the authority to recommend dose or regimen modifications for safety concerns and will provide recommendations about stopping or continuing the trial. To contribute to enhancing the integrity of the trial, the DSMB may also formulate recommendations relating to the selection/recruitment/retention of subjects, their management, improving adherence to protocol-specified regimens and retention of subjects, and the procedures for data management and quality control.

Details regarding the DSMB, procedures, responsibilities, membership, meeting intervals and data to be evaluated will be further described in the study specific DSMB Charter. A written summary documenting the results and recommendations of each DSMB meeting will be maintained on file with the Sponsor.

## **8. SELECTION AND WITHDRAWAL OF SUBJECTS**

Approximately 10 adult subjects with localized scleroderma/morphea will be enrolled in the study at approximately 2 investigative sites in the US.

Subjects must meet all of the inclusion criteria and none of the exclusion criteria at Screening and Day 1 to be considered eligible for participation in this study.

Protocol violations from inclusion and exclusion criteria are prohibited because ineligible study subjects can potentially jeopardize the scientific integrity of the study, regulatory acceptability, or subject safety.

### **8.1. Subject Inclusion Criteria**

A subject must meet all of the following criteria to be eligible for treatment in this study:

1. Subject is an adult,  $\geq 18$  years of age at Screening, with moderate to severe localized scleroderma/morphea with sclerotic lesions which have been unresponsive to standard of care therapy.
2. Subject has stable control of localized disease (clinically inactive) over the 3 months prior to Screening and through Baseline (Day 1).
3. Subject has not participated in previous clinical research study in the 3 months prior to Screening and through Baseline (Day 1).
4. Subject has provided informed written consent.
5. Female subjects of childbearing potential and male subjects engaging in sexual activity that could lead to pregnancy agree to use of at least one of the following adequate birth control regimens while in the study and for 3 months after study medication (FCX-013 or veledimex) is administered:
  - Male partner with vasectomy
  - Male condom AND partner use of one of the contraceptive options below:
    - Spermicide
    - Intrauterine device or intrauterine system
    - Oral contraceptive, either combined or progestogen alone
    - Contraceptive subdermal implant (e.g., Norplant®)
    - Injectable progestogen (e.g., Depo-Provera®)
    - Contraceptive vaginal ring (e.g., NuvaRing®)
    - Transdermal contraceptive patches (e.g., Ortho Evra®)
  - Subjects of childbearing potential who are abstinent agree to use one of the birth control regimens listed if they initiate sexual activity that could lead to pregnancy during the study.

Periodic abstinence e.g., calendar, ovulation, sympto-thermal, post-ovulation methods and withdrawal are not acceptable methods of contraception.

Non-childbearing potential females are defined as females who are premenarchal, or postmenopausal (12 months with no menstrual period without an alternative medical cause), or who have undergone a hysterectomy, bilateral tubal ligation, bilateral oophorectomy (removal of the ovaries), or hysteroscopic sterilization. Documented verbal history from the subject is acceptable.

6. Subject is, in the opinion of the Investigator, able to understand the study, cooperate with the study procedures and willing to return to the clinic for the required follow-up visits.

## **8.2. Subject Exclusion Criteria**

A subject who meets any of the following criteria will be excluded and considered ineligible for participation in the study:

1. Subject has a clinically significant skin disorder other than localized scleroderma/morphea in the anatomical area (e.g., same arm, same side of abdomen) of interest.
2. Subject has localized scleroderma/morphea with potential target lesions only located on the face or over a joint, or lesions that can be successfully managed with topical medications or phototherapy.
3. Subject has symptoms consistent with systemic scleroderma that have not been stable, or that require treatment that has not been stable for 3 months prior to Screening and through Baseline (Day 1).
4. Subject has been treated with UVA1 phototherapy within 2 months prior to Baseline (Day 1).
5. Subject requires treatment with a non-stable regimen of systemic immunosuppressive therapy, for any medical condition, or plans to initiate such treatment during the study period.
6. Subject requires treatment with a non-stable regimen of physical therapy, for localized scleroderma/morphea, or plans to initiate such treatment during the study period.
7. Subject has any medical instability limiting ability to travel to the investigative center.
8. Subject has clinical signs of infection at (or in close proximity to) the target lesion.
9. Subject has a history of, or current, malignancy at/near site of injection (except basal cell carcinoma or squamous cell carcinoma that have been treated).
10. Subject has a history of, or current, clinically significant liver abnormalities.
11. Subject has a history of, or current, clinically significant cardiac abnormalities, or a significant abnormality on ECG, including a QT interval corrected for heart rate (Fridericia; QTcF interval) of > 450 milliseconds in males and > 470 milliseconds in females.

12. Subject has clinically significant laboratory abnormalities which may affect their ability to safely participate in the study.
13. Subject has active infection with human immunodeficiency virus (HIV) as determined by HIV screening, or hepatitis B (hep B) or hepatitis C (hep C), as determined by hep B surface antigen screening, detection of hep C antibodies, or positive result of hep C polymerase chain reaction (PCR) analysis.
14. Subject has an active drug or alcohol addiction.
15. Subject has any known allergy to any of the constituents of the product.
16. Subject has received an interventional chemical or biological investigational study product for the specific treatment of localized scleroderma in the 3 months prior to Screening and through Baseline (Day 1).
17. Subject is pregnant or nursing or plans to become pregnant or nurse during the study period.

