**Table 4: Schedule of Events (Continued)**

**\*include height and weight at Baseline**

**An unscheduled visit, with necessary assessment, may occur as needed.**

Notes:

- a) For any subject who is diagnosed with or dies of a new malignancy, attempts will be made to collect a biopsy of the neoplastic tissue or pertinent autopsy tissue to perform relevant RCL testing.
- b) For any subject with a malignant growth in a region of FCX investigational gene therapy administration, attempts will be made to collect a skin biopsy of the malignant tissue for viral vector presence and potentially clonality of vector integration testing, as available.
- c) In years 1-5 only, a skin biopsy from the region of FCX investigational gene therapy administration (i.e., treated skin area) may be taken to test for relevant transgene and vector persistence *in subjects who consent to the collection of the biopsies required to perform the assay*. However, collection of biopsies will stop if transgene and vector persistence is undetected.

**\*Long-term Follow-Up for years 2-15 may be performed by contacting the subject to review/record requested information, ideally scheduled to follow annual visits and assessment (including relevant laboratory analyses) performed by the subject's health care provider.**

1. Report exposure to mutagenic agents and other medicinal products.
2. Report adverse events of special interest and emergence of new clinical conditions, including, but not limited to: new malignancy, new incidence or exacerbation of a pre-existing neurologic disorder, new incidence or exacerbation of a prior rheumatologic or other autoimmune disorder, new incidence of a hematologic disorder, unexpected illnesses and hospitalization(s).
3. Collection and analysis of a blood sample to monitor for RCL may be performed yearly for up to 15 years. If all post-treatment RCL assays are negative through one year following subject's final investigational product administration, collection of the yearly follow-up samples may be discontinued.

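### Exclusion 9 exempts treated basal and squamous cell carcinoma at the injection site itself, where a recurrence would be tested for vector in skin that received vector-carrying cells

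*Protocol*

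**What the plan says.** **Eligibility.** Section 8.2, criterion 9, excludes a subject with past or current "malignancy at/near site of injection (except basal cell carcinoma or squamous cell carcinoma that have been treated"). It sets no time since treatment, clearance or recurrence-free interval for the exempted tumours.

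**Lesion selection.** Section 9.3 allows up to three candidate lesions, rules out the face and joints, and leaves the final choice to Day 1. It does not mention previous skin cancer.

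**Product and placement.** Section 11.1.1 describes autologous dermal fibroblasts transduced with a lentiviral vector. Appendix 2, step 11, places them intradermally at the edge of the lesion and across the fibrotic area.

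**Testing and consequence.** Section 7.5.1 states: "Any subject diagnosed with a histologically proven skin cancer (including sarcomas) will be biopsied and assayed for viral vector by qPCR". It attaches two consequences to a positive finding:
- "histologically confirmed cancer in combination with the presence of viral vector in the tumor" is one of the "Events that will result in immediate enrollment discontinuation and treatment discontinuation for all subjects".
- In the list of triggers for temporary suspension pending a safety investigation: "A positive result for viral vector will cause product administration to be suspended".

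**Further testing.** Under note b to Table 4, malignant tissue from the treated region is to be sampled, where possible, "for viral vector presence and potentially clonality of vector integration testing, as available". Under note c, a biopsy of treated skin in years 1-5 "may be taken to test for relevant transgene and vector persistence".

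**The concern.** An exception for treated basal or squamous cell carcinoma does little harm in a criterion about cancer anywhere in the body. Criterion 9 is not of that kind. It concerns only the skin that will receive the product, so the exception operates exactly where it can disturb the safety readout.

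These carcinomas can recur. A recurrence in injected skin would go to qPCR. A positive result on that tissue shows that vector is in the sample. It does not show whether the tumour cells carry it or whether injected fibroblasts were cut out with them.

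Safety is the primary objective, follow-up runs for about 15 years, and new malignancy is among the events to be reported. With about 10 subjects, one vector-positive tumour of doubtful origin would weigh heavily in the safety conclusion. A recurrence could be taken for a product effect, or a product effect put down to recurrence.

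**Working it through.** The plan states no figure on this point, so the check sets the provisions side by side.

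1. **Does the exception reach the injected skin?** Yes. Criterion 9 covers only malignancy at or near the injection site, so the exempted tumours are also at or near that site. An untreated carcinoma there still excludes; a treated one does not.

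2. **Does another provision close the gap?** No.
   - Exclusion 1 bars another clinically significant skin disorder in the anatomical area. It does not name a treated carcinoma, while criterion 9 addresses that case and permits it.
   - Section 9.3 lets the investigator choose a different lesion but does not require it.

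3. **Would a recurrence be tested for vector?** Yes, if it is histologically proven. The Section 7.5.1 rule applies to any skin cancer and makes no exception for basal or squamous cell carcinoma or for a recurrent tumour.

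4. **Could the test be positive without vector in the tumour cells?** Possibly. The skin received vector-carrying cells, and note c plans a test for whether vector persists. A positive result from residual product cells needs two things: vector still present when the tumour is sampled, and a tumour lying within injected skin rather than merely near it. The documents settle neither.

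5. **Is there a required step that separates the two sources?** No. Testing for clonality of vector integration could help, but note b makes it conditional on availability and Section 7.5.1 does not link it to the rule. By contrast, the same section requires a positive qPCR for replication-competent lentivirus to be confirmed by a biological assay before FCX-013 administration is discontinued. The tumour rule has no confirmatory step.

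6. **When would it affect the conduct of the trial?** Each subject has one FCX-013 session (Section 9.2) and 14 days of veledimex. The suspension or discontinuation rule has something to stop only while subjects remain to be enrolled or treated. After that, the effect is on attribution alone.

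7. **How large is it?** The documents give neither the number of subjects with such a history nor a recurrence rate, nor how often a recurrence would test positive. No probability can be derived. The one figure available is the weight of a single case: 1 of about 10 subjects, or about 10% of the safety population.

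**The case against.** **The root of the problem lies elsewhere.** Any skin cancer in treated skin raises the same qPCR question, including a first carcinoma in a subject with no history. That comes from Section 7.5.1 and note b, not from criterion 9. This stands. The exception adds to the ambiguity but does not create it.

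**A reader might infer that a tumour at such a site could never be attributed.** The documents do not support that. The product consists of dermal fibroblasts, and histological proof is required. A tumour arising from the injected cells would not be expected to look like a recurrent basal or squamous cell carcinoma. Dermatological history is recorded at Screening (Section 10.3.2), and clonality testing may be available. Attribution becomes harder, not impossible.

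**A reader might infer that one recurrence would end the trial.** The documents do not support that either. Once the last subject has been treated there is no dosing left to stop, and follow-up continues. Section 7.5.1 also routes a vector-positive skin cancer through suspension, a safety investigation and a decision by the data safety monitoring board. It does list cancer with vector in the tumour as a ground for immediate discontinuation as well, so the text gives two answers.

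**A reader might wish to widen the criterion to current cancer at any site.** The reasoning here does not carry over. No product cells are placed at a remote site, so vector found there would not be explained by injected cells in the sample.

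**The investigator can already avoid such a lesion.** True, but nothing requires it. With up to three candidate lesions, requiring it should cost little.

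**Conclusion.** The point holds in a limited form. Criterion 9 admits subjects with a treated basal or squamous cell carcinoma at or near the lesion to be injected, and Section 9.3 does not keep that lesion from being selected. A recurrence there would be assayed for vector, could test positive because of residual product cells, and would be harder to attribute. While enrolment or treatment is still open, it could also trigger the suspension or discontinuation rule.

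This rests on two assumptions that the documents neither confirm nor exclude: that vector is still present when the tumour is sampled, and that the tumour lies within injected skin. The likelihood cannot be estimated from the documents. What supports a change is the weight of one doubtful case in so small a safety study, set against a very low cost. It is a worthwhile improvement, not a flaw that undermines the design.

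**What to change.** **Section 8.2, criterion 9:** remove the exception for basal and squamous cell carcinoma as it applies to skin at or near the lesion to be injected. Rewording it to exempt only treated tumours away from the site would achieve almost nothing, because the criterion does not cover those tumours in the first place.

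**Section 9.3:** state that a lesion with previous skin cancer at or near it is not selected. Applied lesion by lesion, this keeps a subject with another suitable lesion eligible.

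**Cost:** a short amendment to two sections. The downside is the loss of a rare subject whose only suitable lesion has such a history.

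**What remains:** a first skin cancer in injected skin would still raise the same qPCR question. Separately, the two consequences that Section 7.5.1 gives for a vector-positive skin cancer, immediate discontinuation for all subjects and temporary suspension, must be reconciled by the sponsor. This point takes no position on which should apply.
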